11.1. Risks to participants: Asthma attack or unwell

There are risks associated with exposing people living with asthma to high air pollution via exercise protocols. Such activities may increase the likelihood of accidental events, with asthma attacks being the most likely.

11.2. Risk mitigation: Asthma attack or unwell

In order to mitigate potential accident events during the study we will take the following precautions:

- The study will only proceed after University Ethics Committee approval and sponsor indemnity
- Our protocol has been devised with people living with asthma and asthma specialist clinicians and researchers from Asthma and Lung UK public and patient involvement (PPI) group.
- Participants will only be recruited if they have mild - moderate stable asthma, as defined by British Thoracic Society Guidelines
- Participants will be screened by a physiologist ([name]) and a second opinion may be sought from [name], a clinician with specialist knowledge in asthma, if required.
- Usual medication will be continued
- The exercise intensity and locations have been selected to be highly representative of day to day exposures, as such participants will not be exposed to unusually high air pollution.
- Participants will be further screened for unstable asthma on the day of exercise exposures
- Basic rescue asthma medication (albuterol and large volume spacer) will always be available at assessment sites, with researchers trained in its use and administration
- Participants will be closely monitored during the exercise protocol and will be repeatedly encouraged to provide feedback about their physical state during the exercise.
- [name] or a nominated respiratory clinician will be available during all exposure testing
- A risk register and an adverse events register will be maintained for the duration of the study

- Accidents will be discussed with the Chief Investigator and reported promptly to the Sponsor as per Good Clinical Practice regulations, and reviewed at study Project Management Group

11.3. Response to Asthma attack or unwell participants:

This section should be read alongside SOP 16 and the field testing risk assessment. If a participant has an asthma attack during the protocol they will be encouraged to use their rescue medication as advised by their physician. Salbutamol inhalers and spacers will be available at the testing site if needed. A researcher on site will be trained in appropriate first aid. Each site has facilities available to make participants comfortable, including toilets, blankets, isolated room, water and food.

In the event of a participant feeling unwell the research team will:

- Calmly reassure the participant and encourage the participant make themselves suitably comfortable.
- The participant will be observed for any signs of distress or breathing difficulty.
- Place a pulse oximeter on the participant and assess oxygen saturation and pulse.
- If required, first aid will be administered by trained researchers.
- If first aid fails to address the situation the team will seek emergency advice.
- All three sites, have been chosen to have unblocked access for emergency vehicles.
- A report will be completed within 48 hours to be discussed with the project management team.

11.4. Risks to participants: Accidental personal data release

As with all human participant research there is a risk of inadvertent release or loss of personal data through incorrect storage of electronic or hardcopy data or through incorrectly transferring or handling data.

11.5. Risk Mitigation: Accidental personal data release

To mitigate this we shall follow best practice guidelines provided in Standard operation procedures (SOP) by our Clinical Trials Unit. Paper records will be stored securely in locked filing cabinets in password locked rooms in the pass-protected Centre for Primary Care and Public Health. Electronic records will be stored in a password-protected study database on a secure server, in the Centre for Primary Care and Public Health. In the study database, personal details (name, address,

date of birth) will be kept separate from research data, which will be identified by a unique study reference number. In tables of data, participants will only be identified by number not by initials or name. Data management procedures will be completed in compliance with the GDPR and trial regulations. Survey reported data will be stored in the QMUL data safehaven, where data will be held in a UK server and access will be facilitated by two factor authentication. Survey software with integrated data validation checks and audit trails will be used to record study data. Any data transfers between QMUL and Imperial College London will be completed via encrypted Secure File Transfer Protocol. All data will be backed-up weekly to ensure data is safeguarded from accidental loss.

11.6. Annual Safety Reporting

The CI will send an Annual Progress Report to the REC and the sponsor using the Health Research Authority (HRA) template on the anniversary of the REC “favourable opinion”.

12. Public involvement

This proposal was designed with input from the Asthma and Lung UK Centre for Applied Research PPI group. Examples of impact the PPI group has already had include:

- Highlighting the need for breaks during the two hour walking task.
- Highlighting the need to make sure roads are matched for traffic flow to mitigate possible confounders of noise and anxiety.
- Discussed acceptability of respiratory tests. PPI group highlighted the peak expiratory flow, FeNO and spirometry will be familiar tests to most potential participants

As the study progresses the PPI group will be invited to project management group (PMG) meetings. The group will collaborate as advisors and partners in the study and are invited to provide unsolicited advice. To ensure the PPI group can provide meaningful advice and guidance the CI will regularly keep them informed of study developments via email. The meetings will follow the EUPATI (European Patients Academy on Therapeutic Innovation) roadmap (<https://bit.ly/3bugCMk>) discussing themes of: Research design and planning, research conduct and operations and dissemination and communication.

13. Data handling and record keeping

13.1. Data management

Survey Lab will be used to store electronic case report forms all data will be held on GDPR compliant databases with integrated data validation checks and audit trails. All collected data will be held on backed up encrypted servers. Any data transfers between ICL and QMUL will be performed via Secure File Transfer Protocols. Paper records, CRFs and consent forms and recruitment logs will be held locally in double locked locations in [name] (QMUL).

Data Sharing: we will comply with HEI policy on data sharing. A copy of study data will be held on the HDRUK BREATHE secure data hub <https://www.breathedatahub.com>. BREATHE's mission is 'Better respiratory health through better connected data'.

13.2. Confidentiality

We shall follow best practice guidelines provided in SOPs by our Clinical Trials Unit. Paper records will be stored securely in locked filing cabinets in password locked rooms in the pass-protected Centre for Primary Care and Public Health. Electronic records will be stored in a password-protected study database on a secure server, in the Centre for Primary Care and Public Health. In the study database, personal details (name, address, date of birth) will be kept separate from research data, which will be identified by a unique study reference number. In tables of data, participants will only be identified by number not by initials or name. Data management procedures will be completed in compliance with the GDPR and trial regulations. Survey reported data will be stored in the QMUL data safe haven, where data will be held in a UK server and access will be facilitated by two factor authentication. Survey software with integrated data validation checks and audit trails will be used to record study data. Any data transfers between QMUL and Imperial College London will be completed via encrypted Secure File Transfer Protocol. All data will be backed-up weekly to ensure data is safeguarded from accidental loss.

13.3. Record retention and archiving

In accordance with the UK Policy Framework for Health and Social Care Research, research records will be kept for 20 years after the study has completed while personal records will be stored for one year after the study has been completed. At the completion of the study data will be moved to a trusted archive centre. At the end of the retention period data will be destroyed in accordance best practice guidelines at the time of destruction.

14. Laboratories

14.1. Central and local laboratories

The air quality supersites are major field observatories owned and managed by [name]'s team at ICL. They are funded by Natural Environment Research

Council and UK government and provide >100m² of indoor and outdoor laboratory space in contrasting traffic and urban background locations and are ideally suited to understanding the sources of pollution affecting the urban environment. They are equipped with high time resolution instrumentation that operates continuously reporting data to national and international air quality networks.

The mobile measurement trailer is a mobile laboratory owned and managed by [name]'s team at ICL. It carries an identical instrument setup to the two supersites and can be used independently or part of a measurement triplicate as in this experiment. It has been used in a number of field campaigns (e.g. ^{24,25} and has recently be deployed to Manchester (UK) and Birmingham (UK) and Barcelona (ES) to quantify NTE.

The laboratories at ICL have a dedicated room for the storage of human tissues under the provisions of the UK's Human Tissue act.

14.2. Sample preparation and collection

Nasal mucus samples will be collected via nasal lavage. Nasal lavages will be performed at three time points, pre and 2-hour post at the field testing sites while the 18 hours-post exposure measure will be collected in QMUL physiology laboratories. Samples will be biobanked in 5 mL aliquots at -80°C at ICL under Human Tissue Act licence 12521 (local Human Tissue Act lead, [name]).

In addition to the nasal lavage sample 4x10mL of whole blood from a single draw *via* venepuncture from a vein in the lower arm will also be collected pre-, 2- and 18-hours post exposure. Blood plasma from these samples will be biobanked in 1 mL aliquots at -80°C at ICL under Human Tissue Act licence 12521 (local Human Tissue Act lead, [name]).

Samples will be collected in disinfected facilities at the field-testing site. Screens will be used to ensure participant privacy.

14.3. Laboratory procedures

Samples across the interval pre- to 1-hour post exposure will be used to examine metal deposition in the nasal airways and the acute release of endogenous constitutively expressed native damage-associated molecular patterns (DAMPs) and alarmins, such as high mobility group box 1 (HMGB1) S100 proteins, myeloperoxidase-DNA complexes (MPO-DNA), reflecting both cellular injury and NETosis induction, plus IL-33 released from damaged epithelial cells and Thymic stromal lymphopietin (TSLP). Here we hypothesise that metal deposition in the nasal airways, reflecting brake (Cu, Ba and Sb), tire (Zn) and road wear (Fe, Al), causes oxidative stress, triggering cell injury, DAMP/alarmin release resulting in an allergic skewing of the airway. This will be examined across the interval pre- to 18-

hours post exposure, through examination of the concentration of panels of Th2 and Th17 cytokines using Cytometric bead array (CBA) technology. This will allow us to examine the immune and physiologic responses observed in the exposed volunteers in relation to: (a) the site classification, (b) the daily variation of ambient metals/metalloid across the sites; and (c) daily variation in the nasal deposited dose of source-specific metals, including tailpipe tracers (V, Ni and Cr). Nasal lavage samples will also be retained as a downstream resource for the quantification of tire wear tracers, which is outside available budget, but aligns with ongoing work within the MRC Centre for Environment and Health at ICL. Urine samples will be retained as a downstream source for the quantification on analgesic use and tire wear tracers, which is outside of available budget but also aligns with the MRC Centre for Environment and Health at ICL

14.4. Sample storage and transfer

Samples will be transferred from the collection sites in London and Luton to ICL in cooler boxes (4°C) using authorized courier services. Upon arrival samples will be stored with HTA approved facilities at -80°C. All transport, storage and disposal protocols will adhere to the College's SOPs, which can be found on the ICL Governance site.

15. Safety reporting

Accident events occurring between visits/questionnaires/sample collections will not be recorded or reported as they are not the aim or focus of this study.

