Participants will be invited to visit one of three field based study sites in a random order. Study sites will be located in walled gazebos next to air quality monitoring sites (managed by our collaborators at ICL) positioned near roads to provide the required air quality exposure. The protocol for the three visits will be identical and each visit will be separated by at least two weeks (washout). Participants will initially provide a urine sample at home and will bring the sample with them to the testing site. To control for participant exposures before testing, a taxi will be provided for the participant. Participants will travel with car windows closed, and air recirculation turned on. Participants will arrive that the study site at 10:00am, and will be joined by up to three other participants. In the first hour the participants will perform the respiratory health assessments and will provide a blood and a nasal mucus sample. After performing all the pre exercise tests participants will wear a heart rate monitor and will commence the exercise protocol (six exercise bouts of 15 minutes separated by fifteen-minute rest periods on a static exercise bike). Half-way through the protocol participants will perform spirometry, impulse oscillometry and FeNO testing. Upon completing the two-hour exercise protocol participants will complete the same battery of health assessments and will provide nasal mucus samples. Participants will leave the assessment area at about 14:00pm. Air pollution measurements will be taken for the duration of the time that the participant visits the exercise location.

24 hours after the exercise protocol participants will visit the QMUL laboratories to perform the health assessment tests again and to provide a mucus sample via nasal lavage, blood sample via venepuncture and provide a urine sample. After repeating this process three times (one visit to each field site) they will receive an expenses payment of £200 and leave the study. Participants will be paid £60 per exposure visit and £20 pre-screening visit. Participants will be paid for each visit they attend and will be paid when they complete participation or withdraw from the study.

9.4. Exposure site selection:

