9.7. Randomization

The study will use a 6X3 Williams crossover inequality test of paired differences.¹⁷ as such the participants will be randomised to a sequence for their exposures to the three sites. Six sequences will be used (ABC/ BCA/ CBA/ ACB/ BAC/ CAB).

9.8. Health effects assessment on exposure visit days:

Participant flow through an exposure session is summarised in figure 2, while participant flow through the study is summarised in figure 3. On the morning of the site visits participants will first provide a urine sample while at home (9:00 am) Participants will be provided with a taxi to the study site. The participants will be transported taxi with closed windows and air circulation enabled, to the exposure sites.

Once at the exposure sites (10:00am-11:00am) baseline spirometry and determination of FeNO and sample collection (4x10 ml blood collection and baseline nasal lavage) will be performed at the field laboratory. At this time a brief health questionnaire will be administered to assess recent asthma control and ensure the volunteer is free of respiratory infection and has not experienced a recent exacerbation of their asthma.

During the two and a half hour exposure and exercise protocol (11:00am-13:30 pm), participants' heart rate will be monitored throughout the exposure period; at the half way point, after sufficient recovery (12:15am) participants will perform spirometry FeNO and Oscillometry. Immediately post-exposure the participants will perform spirometry, oscillometry FeNO and mucus sample collection at the field lab. The following day, volunteers will return for 28-hour post measurements; biosamples, spirometry and FeNO.

IONA: Schedule of assessment and exposure								
	Pre-Study	Screening	3 day pre	Pre	Exposure	Post	24 hour post	3 days post
		Phys lab	Self assess	Field lab	Field lab	Field lab	Phys lab	Self assess
Consent	x							
Exercise test		x						
FeNO		x		x	x	x	x	
Oscillometry		x		x	x	x	x	
Spirometry		x		x	x	x	x	
Asthma control test		x						
QOL: AQLQ		x						
Baseline questionnaire		x						
Daily Symptom Q		x	x	x		x	x	x
PEF Test			x				x	
Personal air quality			x					
Physical activity			x					
Venepuncture				x			x	
Nasal lavage				x		x	x	
Urine sample				x			x	
Heart rate					x			

Figure 2. Flow of participants through IONA study days

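### Section 15 bars accident events between visits from being recorded or reported, which conflicts with section 11.2 and leaves a delayed asthma attack with no stated route to safety oversight

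*Protocol*

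**What the plan says.** Section 15 (Safety reporting) sets a rule: "Accident events occurring between visits/questionnaires/sample collections will not be recorded or reported". The reason given is that such events are not what the study is about. No exception is made for seriousness, relatedness or time since exposure.

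Section 11.1 says of exercising people with asthma in high air pollution: "Such activities may increase the likelihood of accidental events, with asthma attacks being the most likely". Section 11.2 lists precautions against that risk. Two concern records: "A risk register and an adverse events register will be maintained for the duration of the study" and "Accidents will be discussed with the Chief Investigator and reported promptly to the Sponsor as per Good Clinical Practice regulations", followed by review at the PMG. Neither is limited to time on site.

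On timing, section 9.3 says "Participants will leave the assessment area at about 14:00pm" and "24 hours after the exercise protocol participants will visit the QMUL laboratories". Section 9.8 says "The following day, volunteers will return for 28-hour post measurements", and section 14.2 refers to 18 hours post-exposure. Visits are at least two weeks apart (section 9.3). The schedule of assessments in section 9.8 has a daily symptom questionnaire up to the column for 3 days post. At the start of each exposure visit, a short health questionnaire serves to "ensure the volunteer is free of respiratory infection and has not experienced a recent exacerbation of their asthma".

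**The concern.** The harm that the protocol itself calls most likely is an asthma attack, and an attack need not start while the participant is on site. Section 15 turns on when the event occurs, not on when staff hear of it. An attack on the evening after an exposure is therefore excluded from recording and reporting even if it is described at the next-day visit.

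Two things are at stake. First, a cluster of delayed attacks after exposure at one site would have no stated route to the Sponsor, PMG or ISC while further groups are exposed there. The two-week washout separates one person's visits, not one group's visit from the next group's. Second, staff told of such an attack have opposing instructions: section 11.2 points to logging and reporting it, section 15 to doing neither.

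The reason given in section 15 also sits badly with the rest of the protocol. Section 5.2 sets out to test whether clinically important acute asthmatic responses are driven by non-tailpipe particles, and section 14.3 looks for immune effects up to 18 hours after exposure. Those hours include time when the participant has left the site.

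**Working it through.** **Passages side by side**

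| Question | Section 11.2 | Section 15 |
|---|---|---|
| Are events recorded? | Yes, in a register kept throughout the study | Not if they occur between visits, questionnaires or sample collections |
| Are they reported? | Yes, promptly to the Sponsor, with PMG review | No, for the same events |
| Exception for serious or post-exposure events? | None needed | None given |

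Section 15 cannot be read as covering only trivial mishaps. Section 11.1 names asthma attacks as the leading accidental event, and section 11.2 treats accidents under a heading about asthma attacks and feeling unwell.

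**Is there another route?**

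- Section 11.3 has a report within 48 hours, but it closes a list of steps for a participant being attended to at the time (reassurance, observation, pulse oximetry, first aid).
- Section 15.1 (urgent safety measures) works only once a hazard is known.
- Section 11.6, titled Annual Safety Reporting, describes a progress report and no event capture.
- Section 17.2 gives the ISC a role in conduct and progress, with no stated flow of safety data.
- The daily symptom questionnaire, the pre-exposure health questionnaire and same-day screening for unstable asthma can detect worsening and protect the individual. No passage links their answers to the register, the Sponsor, the PMG or the ISC.

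**How much exposure the rule covers**

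- Exposures: 48 participants (section 10.1) × 3 sites = 144, that is 144 / 3 = 48 per site.
- Sessions: a participant is joined by up to three others (section 9.3), so up to 4 per session. 144 / 4 = 36 sessions at least, 12 per site.
- Exposures followed by a later pre-exposure questionnaire: 48 × 2 = 96. Not followed by one: 144 − 96 = 48.

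**Time off site before the next-day visit**

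Exposure runs 11:00 to 13:30 (section 9.10) and departure is at about 14:00. The protocol gives three times for the next-day visit and does not say whether they count from the start or the end of exposure.

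| Stated interval | Clock time next day (from start / from end) | Hours after departure |
|---|---|---|
| 18 h | 05:00 / 07:30 | 15.0 to 17.5 |
| 24 h | 11:00 / 13:30 | 21.0 to 23.5 |
| 28 h | 15:00 / 17:30 | 25.0 to 27.5 |

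The range is 15.0 to 27.5 h, or 21.0 to 27.5 h if the 18-hour figure is set aside.

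**Days without scheduled contact**

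Assume the minimum washout (exposure on day 0, next exposure on day 14), post-exposure questionnaires on days 1 to 3 and pre-exposure self-assessment on days 11 to 13. Days 4 to 10 then have no contact: 10 − 4 + 1 = 7 days. A longer washout lengthens this gap. After the third exposure nothing is scheduled beyond day 3.

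**The case against.** The strongest reply is that the two sections can be reconciled. Most precautions in section 11.2 concern the visit day, and a register kept throughout the study need not cover every hour of a participant's life. On that reading it holds on-site events only and section 15 confirms it. This is possible, but section 11.2 does not say so, and its wording on duration points the other way.

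Second, the team would not be blind. Asthma symptoms are a secondary endpoint collected at 24 hours and up to 3 days post. Reliever use in the six hours before a visit's first spirometry leads to an offer to reschedule (section 9.9), and the PMG, made up of the co-investigators, meets monthly. This stands in part: delayed worsening may be in the study data and informal awareness is possible. But outcome data are not safety reports, and no step from one to the other is stated.

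Third, participants have stable mild to moderate asthma, and section 11.2 describes the exposures as typical of daily life. That bears on how often an attack might occur, not on whether one should be recorded.

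Fourth, SOP 16 and the field risk assessment are not shown and may add reporting steps. They would not by themselves cancel an explicit protocol sentence.

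Finally, the counts measure exposure, not harm, and the 18-hour figure implies a laboratory visit at 05:00 to 07:30. Both remarks are fair. The conclusion needs neither the hours nor the day count.

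**Conclusion.** The concern holds and should be fixed. Section 15 is an affirmative instruction, not a silence that another document could fill. Followed as written, it removes from safety reporting a delayed attack of the kind that section 11.1 expects most.

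The rule applies after each of 144 exposures in at least 36 sessions. After 48 of them, scheduled contact ends with the 3-day questionnaire and no later pre-exposure check follows. The number of attacks that would go unreported cannot be estimated, because the protocol gives no event rate. The seven days without contact rest on the minimum washout and on the assumed mapping of the 3-day columns. That no route exists is a statement about the protocol text only.

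**What to change.** Reconcile sections 15 and 11.2 by replacing the section 15 sentence. State that asthma attacks, unscheduled care, oral corticosteroid courses and hospital attendance reported at any scheduled contact (next-day visit, 3-day questionnaire, next pre-exposure questionnaire) are entered in the section 11.2 register with the exposure site and the time since exposure, reported to the Sponsor, reviewed by the PMG and ISC, and tabulated by site. State the same event window in section 11.2. The exact event list is for the sponsor to settle; what is essential is one consistent scope and a stated route.

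Add a questionnaire item only if the existing forms do not already ask about these events. The change uses contacts already scheduled and sets no rule of clinical management. Its cost is a protocol wording change, possibly one questionnaire item, and slightly more event-reporting work.
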